Again, mixed methods are employed. As the first implementation does not employ a diversion the system is somewhat hidden from patients – as they will attend their usual secondary care setting. However, the use of threshold rejections in the first implementation will be assessed by postal questionnaires to all patients for whom their referral was rejected and a proportion of others sent to secondary care to establish a baseline level of satisfaction and cost. In implementation level two an initial postal questionnaire again will be sent to all patients processed through the referral management system. These questionnaires (previously used by BIRCH, Christell H et al) will be used to collect the primary data on costs incurred by patients and patient carers including out of pocket costs associated with public transport fares, private transport and parking and time spent travelling to and from, and

¹ It is recognized that these individuals may reside in the NHS NCB

Version 2 15 September 2015

waiting and being treated at, the facilities. Patients will be asked, within the questionnaire for consent to view their dental treatment records. From those consenting, a clinical case review will be undertaken to establish; for each case:

- Treatment provided vs. treatment requested on referral form
- Accuracy of referral information and any errors detected (for example on the medical history)
- Any adjunct sedation used whether requested or not
- Number of sessions of treatment required to complete the course of treatment
- Any complications of the treatment requiring further clinical intervention
- Number of review appointments

The research team ([name]) has recently developed a data collection tool for such case note review as this has been deployed in an assessment of referral and triage management of child general anaesthetic cases.

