Qualitative in-depth semi-structured interviews will be conducted with a sample of patients selected from each triage group (specialist primary care & secondary care) to ensure maximum variation according to parameters such as age, gender, socio-economic status and according to outcome of the triage system, in terms of the treatment pathway followed. We estimate we will interview between 20-30 patients for this part of the study. Patients will be interviewed very early in the process as close to point of referral as possible and will be followed up further down their care pathway in order to explore their experience and views about the treatment decision made. An iterative approach to data collection will be adopted as in previous phases to allow for intermittent analysis and further sampling where necessary. For example, further patients will be sampled later implementation 2 to ensure we include some cases where the decision may have been problematic and to explore a range across the triage groups. The main focus of these interviews will be an in-depth analysis of service user experience, as well as understanding and perceptions of quality and safety regarding service provision. Personal histories of dental service experience will be elicited, and patients will be asked to reflect on good and bad experiences, changes in the system, and markers of good quality service and care.

How does RCRM impact on the NHS? Whole Service Assessment & making change happen

This final stage of the project takes a holistic view of the project and will ensure that unintended consequences are not missed. Referral management is complex process that interfaces with primary and secondary care providers, each of which has different drivers, incentives and ambitions. A need to recognize this and ensure that stakeholders are properly heard is essential to the process of change management within dentistry.

A. Selection practices

Version 2 15 September 2015

All General Dental practices and acute trust providers within NHS Sefton will be involved in data capture, with settings sampled purposively for qualitative research, as outlined above.

B. Screening and Selection of Subjects

Patients

During implementation 1 & 2 *all* patients referred from GDPs in Sefton will be triaged and processed via the referral management system. Prospective study participants will be identified via the referral management centre and assessed for eligibility by [name].

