All participants must have been appropriately referred for MOS and consented to the study (please see participant flow diagram, appendix 2). Participants will be asked to provide consent for the following:

- i) For the research team to see their referral notes (example below)
- ii) To complete a questionnaire
- iii) To take part in a semi structured, qualitative interview
- iv) For the research team to view records held by their GDP (for follow up purposes)

Participants will be given a choice of face to face or telephone interviews. For the face-to-face interview participants will be given a choice of venue, either at the University of Manchester, a community venue such as café or in their homes. Interviews will be carried out towards the end of stage 2 and during phase 3 (implementation stages).

Patient information sheets will be sent to participants direct from the referral capture centre following receipt of their referral in order to allow participants sufficient time to decide if they would like to participate in the study. Following their clinical consultation at either specialist primary care or secondary care clinics, eligible patients would be advised by their treating clinician they were eligible for the study and, if they wished to consent, a research nurse was available to take this and answer any further questions they might have. The consent process with the CRN Research Nurse will take place in a non clinical setting within the hospital. Patients would be under no obligation to see the CRN staff and may leave the appointment without further contact. The treating clinician will remind the patient that they are under no obligation to participate and nor will their on-going care be affected by their decision.

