For the minority of Sefton patients who chose to attend a secondary care clinic other than Ormskirk District General, patient information sheets and consent forms will be sent to participants direct from the referral capture centre following receipt of their referral, with stamped addressed envelopes enclosed to facilitate the return of consent forms. Following receipt of consent forms, participants will be sent questionnaires designed to collect baseline data, in time to coincide with their oral surgery consultation appointment. These questionnaires are to be completed after the consultation has taken place, so that patients will have an accurate idea of costs incurred. This system is required as some clinics have low number of eligible patients and hence cannot be staffed viably by CRN personnel. The ability for potential participants to ask questions of the research team is facilitated by the provision of telephone and email contact information.

Participants will be offered a gift voucher to the value of £10 to be redeemed with Amazon or a similar retailer on receipt of their questionnaire. This is to thank them for to completing the questionnaire and take part in the study.

Professionals

NHS commissioners, Acute Trust Staff and General Dental Practitioners will be approached by a member of the research team, either by telephone or face to face during the course of the study. Consent will be sought from these professionals prior to taking part in any interviews or focus groups.

Version 2 15 September 2015

C. Monitoring of the study

This study will be monitored by Staff from the University of Manchester Dental Health Unit, at periodic intervals by the principle investigator and consultants to ensure that the study is being conducted according to Good Clinical Practice Guidelines. NHS guidelines regarding 18 week waiting times will be adhered to.

G. Randomization

No randomisation necessary, a census approach will be adopted, which encompasses all practices and acute trust providers within NHS Sefton.

H. Outputs

Referrals Method

Patients' understanding of treatment pathway

Number and ultimate destination of referrals

Data monitoring

Number and reasons for DNA appointments Data monitoring/ questionnaire/ interviews

Rejected referrals

What happened? Data monitoring/ interviews

Costs

Understanding of treatment pathway Interviews
Quality of data Data monitoring
Time of referral to appointment Data monitoring

XI. DATA ANALYSES

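### The protocol promises patient-reported data on rejected referrals and non-attendance, but its consent procedure describes no way in for rejected patients or, on the main route, for first-visit non-attenders

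*Protocol*

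**What the plan says.** **Promised data.** Under How does RCRM impact on patients?, threshold rejections in implementation 1 are to be assessed by "postal questionnaires to all patients for whom their referral was rejected", together with a proportion of patients sent on to secondary care, to give a baseline for satisfaction and cost. In implementation 2 an initial postal questionnaire goes to everyone processed by the system. H. Outputs has the line "Number and reasons for DNA appointments Data monitoring/ questionnaire/ interviews". For what became of rejected referrals it lists data monitoring and interviews, with no questionnaire.

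**Consent.** Under B. Screening and Selection of Subjects, "All participants must have been appropriately referred for MOS and consented to the study". The items needing consent include "To complete a questionnaire". Information sheets are posted when the referral is received, but on the main route the study is raised later: "Following their clinical consultation at either specialist primary care or secondary care clinics, eligible patients would be advised by their treating clinician". A research nurse then takes consent: "The consent process with the CRN Research Nurse will take place in a non clinical setting within the hospital". The same section posts consent forms at referral receipt only to the minority who choose a hospital clinic other than Ormskirk. Their questionnaire is still to be filled in after the consultation.

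**Patient interviews.** The sample is to be "selected from each triage group (specialist primary care & secondary care"), and "Patients will be interviewed very early in the process as close to point of referral as possible".

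**The concern.** The plan for collecting patient data and the plan for obtaining consent describe different populations. The first covers everyone who passes through the system and singles out those turned away. The second, followed literally, reaches people whose referral was accepted and who, with a narrow exception, came to clinic.

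This matters because the effect on patients is one of the four main questions in Purpose of this study. The protocol notes that, without diversion, patients see little of the system in implementation 1, so rejection is the main way it reaches them in that year. The questionnaires also supply the patient costs that Cost effectiveness adds to service costs as a proxy for societal cost. Data not collected from a group cannot be recovered in the analysis.

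**Working it through.** No formula applies. The check follows each patient group through the written consent routes and compares the result with what is promised.

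**Inputs**
- Formal inclusion criteria (VII. Subjects): referral for oral surgery, ability to consent, adult age. The word *appropriately* does not appear.
- Implementation 1 section: referrals below the threshold are returned, so no consultation follows from that referral as it stands.
- Consent conditions, timing and place: B. Screening and Selection of Subjects.
- Promised data: How does RCRM impact on patients? and H. Outputs. The outputs table is flattened in the text available, so its lines are read as they stand.

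**Trace by group**

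1. *Rejected.* These patients have no clinic contact at which consent could be sought. They are outside the postal minority, which is defined by attendance at another hospital clinic. They may fail the appropriate-referral condition, and the interview frame does not name them. Consent route described: none. Promised: a questionnaire to all of them in implementation 1, and inclusion among all processed patients in implementation 2.

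2. *Accepted, main route, never attends a first consultation.* The patient receives an information sheet but never meets the clinician or nurse. Consent route described: none. Promised: the general questionnaire in implementation 2, and reasons for non-attendance from questionnaire and interviews.

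3. *Accepted, postal minority, never attends.* Consent can be given before the appointment, so there is a way in. However, the questionnaire is to be completed after a consultation that did not happen.

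4. *Accepted and attends.* Both routes work. On non-attendance, these patients can report only appointments missed before or after the visit they attended. Those on the main route can be interviewed only after the consultation, which sits badly with the aim of interviewing close to referral.

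**Result.** Groups 1 and 2 have no described consent route although data from them are promised. Group 3 has a route with a questionnaire timed for other people. Only group 4 is properly served.

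**Two related mismatches.** The patient-impact section seeks consent to view treatment records inside the questionnaire, whereas the selection section lists GDP-held records and the questionnaire itself as consent items. Recruitment is described at specialist primary care clinics as well as hospitals, yet nurse consent is placed in the hospital.

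**Size.** The protocol gives no rejection rate and no non-attendance rate. Two pilot figures might look like substitutes but measure other things. The 9% in NHS Manchester is a fall in referrals across all dental specialties. The 7 of some 600 diverted patients (7/600 = 1.2%) refused the selected provider. No excluded percentage can be derived.

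**The case against.** Several points on the other side are sound.

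- *Not all consent follows the consultation.* A reader might infer that it does. The postal minority return forms beforehand, so a few non-attenders could be admitted. That route admits no rejected patients.
- *The patient-impact section implies a mailing that needs no clinic visit.* It does, so the text can be read as two unreconciled procedures and not as deliberate exclusion. But the selection section makes the questionnaire conditional on consent and gives this mailing no consent step.
- *Appendix 2 holds a participant flow diagram that is not shown.* It may draw another route. The text describes none and would still need to agree with it.
- *Appropriately referred is ambiguous.* It need not mean accepted at triage, and the formal criterion asks only for a referral. The lack of a consent route for rejected patients does not depend on this reading.
- *Other sources cover these groups in part.* Dentist interviews ask what happens to rejected patients, and practices with many rejections are targeted. Data monitoring is listed for both non-attendance and rejection. The outputs table does not say whose interviews it means for rejected referrals, so dentists could satisfy that line. This information is second-hand and does not replace the promised patient questionnaires.
- *Interview sampling aims for variation by triage outcome and adds problematic decisions later.* That could be stretched to include rejected patients, but the two named groups do not include them.
- *Non-attendance may be temporary, and returned referrals may be completed and accepted.* Both are possible, so the gap concerns those who never reach a first consultation.

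**Conclusion.** The contradiction stands. Followed as written, the consent procedure leaves out rejected patients and main-route first-visit non-attenders, whom the plan says it will survey. The questionnaire, patient-cost, satisfaction and patient-interview data would be selected towards accepted attenders. Severity is moderate and confined to secondary data.

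A reader might go further in three ways that the documents do not support.

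- *That the main result is compromised.* The primary outcome is the number and destination of referrals, with rejected as a category. It comes from routine data and needs no patient consent.
- *That patient impact would be measured only where the system worked, and so be biased in its favour.* Attenders include misdirected patients and those with complications. The direction of any bias cannot be derived.
- *That a stated share of patients is lost.* Any percentage would rest on rates the protocol does not give.

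The conclusion assumes that the text governs and that the flow diagram in appendix 2 adds no separate route.

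**What to change.** 1. Extend the existing postal consent, sent at referral receipt, to rejected patients and to those who do not attend. Keep the clinic nurse route for attenders.
2. Align the eligibility sentence in the selection section with the formal inclusion criterion, so that triage outcome does not exclude anyone.
3. Adapt the questionnaire and its timing for patients with no consultation.
4. Name rejected patients as a group in the interview sampling frame.
5. While amending, reconcile where consent for record access and for the questionnaire is obtained, and check appendix 2 against the text.

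If this is not done, withdraw the promised patient-reported data on these groups and limit the patient-impact conclusions to accepted attenders.

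The cost is an ethics amendment and postage. The downside is a lower response by post than face to face, so response should be reported by triage outcome. The protocol's staffing reason for using post at low-volume clinics is not disturbed, because the nurse route stays where it is.

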The introduction of the 2006 dental contract provided a Band II payment for tooth extraction that, on North West averages, provides a fee of £75 for one or more teeth to be extracted within a single course of treatment. Figures from acute trusts and eReporting data suggest an exponential increase in referrals of MOS to secondary care. There are a number of reasons postulated for this including perverse incentives in the dental contract (GDPs receive payments for referrals alone at the same Band II level) and that younger dentists may have limited competency as undergraduate experience in MOS treatments is limited (MEE Report, 2010). A number of acute trusts in the North West have struggled to deliver capacity against this increase in demand and work has been undertaken to manage this through a number of routes and approaches.

Current demand management strategies for MOS – NHS Manchester

NHS Manchester has continued the early work started in NHS Trafford with the introduction of the hybrid referral management pilot. All referrals to secondary care are captured (either by post, email or fax) and then scanned for paper-based triage. A website provides practitioners with a live status check on their referral's progress. This work has taken place under the Dental QIPP programme stream in the North West for demand management. By producing an agreed proforma, requiring adherence to a minimum dataset (including provision of appropriate radiographs) and ensuring administrative procedures to check compliance, there has been a 9% reduction in referrals into all dental specialties as well as the diversion of considerable numbers of referrals into primary care and advanced primary care settings. It is important to recognize that, given the drive to decrease costs whilst improving quality of care across the NHS, referral management systems are developing rapidly.

NEED

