This is a before and after methodological approach, which will involve collection of baseline data over 12 months, followed by staged implementation. Implementation will take place over two phases: a sandbox, or virtual implementation of the system (referral decisions made by GDPs will be captured, however all patients will ultimately be treated in secondary care) followed by full implementation of the system, (appropriately referred patients being treated in both primary and secondary care settings).

The pilot study suggests that changes in referral behaviour can be detected as early as three months following the introduction of a management system. The cost reductions seen by triage diversion are seen immediately. However, in order to understand the long-term implications of the referral system, including any reactive behaviour by GDPs or Secondary Care providers we are proposing to run the introduction of the system for 12 months and the full diversion service for a further 12 months. This should allow a full financial year's worth of cost data to be assessed as well as determining the degree of adaptation to the system. The time period will also enable a robust assessment of primary care treatment quality – i.e. there will be sufficient time to determine if cases treated in primary care return to secondary care for additional or remedial treatment as well as tracking seasonal variations in

Version 2 15 September 2015

referrals. For example we have noted decreases in referral volumes around December and January (relating to the holiday period) and increases in volumes round March (relating to end of financial year).

Implementation 1: Virtual Referral management without diversion (year 2)

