The quantitative analysis has been designed to evaluate the impact of a change in service, with the primary analysis using a piecewise regression / interrupted time series analysis (ITS) design. This is an appropriate methodology to evaluate the effects of a change in service delivery. Whilst it is acknowledged that the lack of a concurrent control group can be considered a weakness (Brown & Lilford, 2008), the nature of the investigation and implementation precludes such a design. The proposed study design and analysis will aim to minimize threats to internal validity (Ramsay et al, 2003): A single PCT boundary (NHS Sefton) with a diverse practice and patient profile has been identified for study; lengthy evaluation pre-intervention and during two stage implementation over three years will address any concerns regarding secular trends (Brown & Lilford, 2009). Additionally, trends observed in Sefton over the implementation period with be compared with national trends in oral surgery referrals through the examination of Hospital Episode Statistics (HES) data. This design will enable 24 months of referral management assessment during the study, and thus captures and enables the measurement of seasonal variations in referral patterns. Further, a large intervention effect has been observed in an earlier pilot study, with a re-direction of MOS referrals from secondary care to primary care based services of over 68% (data from Central Manchester Foundation Trust). The primary outcome measures will be the monthly reported number and ultimate destination of referrals from baseline through to six months, implementation stage 1 referral management alone (12 to 24 months) and Implementation stage 2, referral management with diversion (24 to 36 months). Analysing monthly data has a number of advantages: it enables the cyclical nature of referrals observed in the pilot study to be accounted for; will illustrate whether referral management alone (the process of collecting, assessing and administratively triaging referrals in the absence of diversion) results in a decrease in referrals into secondary care; short-term changes will not be missed; any observed effect is maintained or return returns to original levels. The principal analysis will be to determine whether the implementation of the Referral Management System with diversion has an effect that is significantly different from any underlying secular trend.

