Statistical analysis will be undertaken using time series regression models. Pre-intervention and post-intervention (virtual and actual implementation) trends will be evaluated. In addition, the pre and post intervention effects at Sefton will be compared with national trends in order to further investigate the effects of possible secular trends. Analysis and reporting will be undertaken according to recommended quality criteria (Ramsay et al, 2003). The best fit pre intervention and post intervention lines will be estimated using linear regression and autocorrelation will be adjusted for by using the maximum likelihood methods where appropriate (Draper & Smith 1981). First order autocorrelations will be tested for statistically using the Durbin – Watson statistic and higher – order autocorrelations will be investigated using the autocorrelation and partial autocorrelation function.

Two effect sizes will be estimated. First, a change in level of outcome at the first point of after the introduction of the intervention will be estimated for each of the referral outcomes (Primary Care, Secondary care, DWSPI, rejected). This will be carried out by extrapolating the pre intervention regression line to the first post intervention point. The difference between this extrapolated point and the post intervention regression estimate for the same point will represent the estimated change in level of referrals. Secondly, a change in the slopes of regression lines will be investigated by calculating the post intervention minus pre intervention slope. The difference observed for each change will be further investigated for statistical significance.

Data will also be presented descriptively and graphically on the number and nature of referrals according to the referral destinations of rejected, primary care, primary advanced or secondary care.

Version 2 15 September 2015

Any trends observed for referrals to secondary care for Sefton will be compared with national trends using Hospital Episode Statistics (HES), which will be obtained via NHS Sefton and analysed for statistical significance at each recorded time point.

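### The level change is estimated from straight lines with no seasonal term over three 12-month phases, so the seasonality the protocol reports can bias it by about as much as the 9% reduction it cites

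*Protocol*

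**What the plan says.** In Section IX (Interrupted time series study) the protocol plans "collection of baseline data over 12 months, followed by staged implementation" and then proposes to "run the introduction of the system for 12 months and the full diversion service for a further 12 months". The same section records the seasonality already seen: "we have noted decreases in referral volumes around December and January (relating to the holiday period) and increases in volumes round March". It gives neither the size of these swings nor the calendar month in which the study starts.

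In Section XI (Quantitative data analysis) it says that the 24 months of referral management "captures and enables the measurement of seasonal variations in referral patterns", that monthly data allow the cyclical pattern to be accounted for, and that "lengthy evaluation pre-intervention and during two stage implementation over three years will address any concerns regarding secular trends".

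The estimator follows in the same section: the "best fit pre intervention and post intervention lines will be estimated using linear regression", with autocorrelation tested and adjusted for. Two effect sizes are declared. One is the change in level, meaning the post line minus the projected pre line at the first post point. The other is the change in slope. No seasonal term is named. National Hospital Episode Statistics (HES) data are a separate comparison, not a term in the model.

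**The concern.** When every phase lasts one year and starts in the same month, the seasonal pattern tilts each fitted line by the same amount. The lines then form a 12-month sawtooth, and each tooth reads as a level change at the break even if the intervention does nothing. Adjusting for autocorrelation does not remove a fixed calendar pattern.

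The level change is the first of the two declared effect sizes. It is most exposed at the first break, where the protocol asks whether referral management without diversion reduces referrals to secondary care. The only figure it cites for fewer referrals under a management system is 9% (Section I, NHS Manchester, all dental specialties). A seasonal artefact of that order could imitate such an effect or hide it. The assurance about measuring seasonality could also lead an analyst to add month terms to the 36 months, which does not identify the level change.

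**Working it through.** The protocol gives no standard error or power for the level change, so there is no figure of its own to reproduce.

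**Inputs from the protocol.** Phases of 12, 12 and 12 months; a dip in December and January and a rise in March; straight lines by linear regression; the definition of the level change.

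**Assumptions.** Breaks at months 13 and 25. The same additive seasonal pattern every year and no intervention effect. Dip and rise of equal size, 10% or 20%, with an ordinary month set to 100 referrals. All 12 start months are tried.

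**Bias formula.** Let b be the least-squares slope of the seasonal pattern over positions k = 1 to 12, and m its mean. The fitted line in each phase is m + b(k - 6.5).
- Pre line projected to the next month (k = 13): m + 6.5b.
- Post line at its first month (k = 1): m - 5.5b.
- Level change: (m - 5.5b) - (m + 6.5b) = -12b, the same at both breaks.
- Slope change: b - b = 0. Difference between the two level changes: 0.

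**Numbers, 20% swings.** b = sum of (k - 6.5) times the deviation, divided by 143.
- February start (December, January and March at positions 11, 12 and 2): b = [-20(4.5 + 5.5) + 20(-4.5)]/143 = -290/143 = -2.03; bias +24.3.
- December start (positions 1, 2 and 4): b = [-20(-5.5 - 4.5) + 20(-2.5)]/143 = 150/143 = 1.05; bias -12.6.
- April start (positions 9, 10 and 12): b = [-20(2.5 + 3.5) + 20(5.5)]/143 = -10/143 = -0.07; bias +0.8.

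| Dip / rise | Lowest (December start) | Highest (February start) | April start |
|---|---|---|---|
| 10% / 10% | -6.3 | +12.2 | +0.4 |
| 20% / 20% | -12.6 | +24.3 | +0.8 |

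With unequal swings an April start gives +5.5 (20% dip, 10% rise) or -4.2 (10% dip, 20% rise).

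**Full month terms on 36 months.** Intercept, time, two level changes and two slope changes make 6 columns; 11 month terms make 17. Time minus 12 times each level-change indicator runs 1 to 12 in every phase, so it is itself a calendar-month function. The rank is therefore 16 of 17. The baseline slope and both level changes are not estimable. The slope changes and the difference between the level changes are.

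**Specifications that are estimable.** Standard errors (SEs) of the level changes at the first and second breaks, in units of the residual SD s, with independent errors:

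| Model | Rank | SEs |
|---|---|---|
| 36 months, no seasonal term | 6 of 6 | 0.82s, 0.82s |
| 36 months, December/January and March indicators | 8 of 8, every start month | 0.83s to 1.01s at both breaks |
| 12 earlier months, month terms | 17 of 17 | 0.90s, 1.16s |
| 24 earlier months, month terms | 17 of 17 | 0.75s, 1.03s |
| All 39 study months, month terms | 17 of 17 | 1.23s, 1.05s |

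For the seasonal pattern the protocol describes, the two-indicator model has zero bias at both breaks.

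**The case against.** A reader might infer that season and intervention are wholly inseparable here and that the claim to measure seasonality is simply false. The documents do not support that. Only one component of the month effects, the within-year sawtooth, is aliased. The second declared effect size is unbiased under exact alignment. The particular dip and rise in Section IX can be estimated from the existing 36 months with two indicators.

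Other points for the plan:
- **The seasonal term may sit in a SAP.** The protocol does intend to account for cyclicality, and the form of the term is commonly left to a SAP. That answers the mere absence of a term. It does not answer the point that unrestricted month terms, a usual choice, fail on these phase lengths.
- **Alignment is not certain.** Months 12 and 24 each fall in two phases as written. Breaks at those months restore full rank with month terms, but the SEs rise to 1.62s and 1.44s, and the unadjusted lines remain biased (-12.5 to +26.6 at the first break for 20% swings). Section XI also mentions a baseline to six months; on either half of the baseline year the rank stays at 16 of 17.
- **The size is assumed.** With 10% swings the bias exceeds 9 per 100 for only two of the 12 start months, February and March. The 9% comes from another area and all specialties.
- **The principal analysis concerns diversion**, where the pilot redirection was over 68%, well above the bias found. Destinations that do not exist before diversion begins are also not described by the -12b formula at that break.

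All of this stands, and it limits the severity. It does not make the straight-line level change sound. Harmonic terms are a weaker way out: one to three pairs are estimable, but they multiply the SE by 1.35 to 2.14 and fit a narrow dip and spike poorly.

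**Conclusion.** The concern holds for the level change only, and should be fixed. As written, the first declared effect size carries a seasonal bias of -12b: about -6 to +12 per 100 ordinary-month referrals for 10% swings and -13 to +24 for 20%, of either sign, and possibly near zero. This rests on aligned 12-month phases, a stable additive pattern, and amplitudes and a start month that the protocol does not give. The result most at risk is the effect of referral management alone. Nothing here suggests that seasonality could account for a redirection of the size seen in the pilot. The seasonality assurance in Section XI is too strong for the level change, but not empty.

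**What to change.** 1. In Section XI, add pre-specified indicators for December/January and for March to the segmented model. This uses 2 degrees of freedom and raises the level-change SE from 0.82s to at most 1.01s at the same s. It assumes no other month effects, and the plan should say so.
2. Where monthly data for the same outcome can be had, lengthen the series and fit common month-of-year terms. This uses 11 degrees of freedom, with the SEs tabulated above. The introduction says that "Figures from acute trusts and eReporting data suggest an exponential increase in referrals of MOS to secondary care", which shows that some historical figures exist but not that monthly Sefton counts by destination do. This step is therefore conditional and should not replace the first.
3. State the calendar start month and assign months 12 and 24 to one phase each, since both determine what can be estimated.
4. Qualify the seasonality claim: the design supports a restricted seasonal adjustment of the level change, and full month effects only if the series is longer than three aligned years.

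The main cost is model wording and a modest loss of precision, part of which should return because removing seasonal variation lowers s.
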